5.1.5 Patient Disposition

Patient disposition will be summarized as indicated below using the Enrolled Analysis Population. The disposition categories will be summarized by number and percentage using the number of enrolled patients as a percentage denominator:

- Enrolled patients
- Safety population
- Evaluable population
- Completer population
-

Patient disposition information will be listed. In addition, patients who were discontinued from the treatment or who did not complete the treatment will also be presented in this listing, including early termination reason. A subject is considered a statistical completer (Evaluable population) if he/she receives at least 2 weeks of study treatment and completes the Week 3 Wound-QoL questionnaire.

5.1.6 Protocol Deviations

Protocol deviations will be listed as well as summarized and grouped into different categories such as

- Violation of inclusion/ exclusion criteria
- Time schedule deviations
- Non-compliance based on the investigator or designee's compliance records in eCRF.
- Missing essential data such as incomplete wound-QoL questionnaire data
- Patient not discontinued as per protocol of study (in case of infection or treatment with prohibited medication)
- Other non-compliance

Multiple deviations can occur in the same patient and thus a patient can be counted in more than 1 deviation category.

Patient listings of protocol deviations will include reasons for non-compliance and will be sorted by site.

5.1.7 Demographics and Baseline Wound History Characteristics

Patients demographics are age [years], weight [kg], height [cm], body mass index (BMI) [kg/m²], sex, race, and ethnicity.

All data as recorded in the eCRF are used for the analyses of patient demographics.

Regarding age, the age at the time of the baseline visit is recorded in the eCRF.

Categorical patient baseline wound history variables are:

- 1) Wound type
 - Venous Ulcer
 - Arterial Ulcer
 - Diabetic Ulcer
 - Burn (1st or 2nd Degree)
 - Cellulitis
 - Soft Tissue Necrosis
 - Neuropathic Ulcer
 - Traumatic Ulcer
 - Collagen Vascular
 - Infectious

- 2) Wound description
 - Partial Thickness Wound
 - Full Thickness Wound

- 3) Wound location
 - Left leg
 - Right leg
 - Left foot
 - Right foot

4) Wound location on the leg or foot

- Medial
- Lateral
- Anterior
- Posterior

5) Past complications

- Infection
- Recurrent Hospitalizations
- Others

Patient demographic and baseline background information will be summarized in tables for the safety, evaluable and completer population.

Descriptive statistics (sample size, mean, median, standard deviation [SD], minimum [Min] and maximum [Max]) will be presented for continuous variables: age, body mass index [BMI], height, weight, wound age, and wound surface area. Frequency counts and percentages will be tabulated for categorical variables: gender, ethnicity, race, and baseline target wound history and characteristics categories. As each subject may have 2 chronic wounds, which will be treated and assessed, we will need to distinguish between the 2 wounds for the purpose of descriptive analysis (i.e. wound #1 and wound #2). Baseline target wound characteristics will also be listed in order to include a description of other past complications. Only 1 wound must meet all of the inclusion/exclusion criteria.

5.1.8 Treatment Exposure

Administration of study treatment in the clinic will be performed by the Investigator or designee, ensuring compliance with the individual patient's regimen.

Exposure in terms of administered Prontosan solution and Prontosan gel will be listed and summarized descriptively by week for the safety population.

5.1.9 Prior and Concomitant Medications and Therapies

Prior medications are defined as those taken by or administered to the patient before screening and up to the first study treatment. Concomitant medications are defined as those taken by or administered to the patient after the first study treatment.

Medications will not be coded and only listings of reported terms will be presented.

In case of incomplete stop date a medication or therapy will be considered as prior if this can be concluded without any doubt. All other cases will be considered concomitant medication or therapy administered during the 4-week treatment period.

The medication indication, the regimen, start and stop date will be displayed. The listings will differentiate between prior and concomitant medications in the safety population by the order of the medication/therapy start date.

5.1.10 Medical Histories

The assessment of an illness being previous or concomitant is entered directly in the eCRF by the investigator.

Prior illnesses that the patient has experienced prior to signing the Informed Consent Form (ICF); this is the patient's previous illnesses. New illnesses present after the ICF is signed and up to the time of first treatment (Week 1) are to be regarded as concomitant illnesses.

Illnesses are not coded by Medical Dictionary for Regulatory Activities (MedDRA). All medical history data will be presented in a patient data listing.

Medical history will be displayed separately for prior and concomitant illnesses in the safety population.

5.2 Statistical Analysis

In this phase IV study, statistical analysis will focus on clinical outcome assessments. The clinical outcome assessments include patient-reported Wound-QoL questionnaire, and investigator-reported wound(s) size and assessments.

5.2.1 Primary Analysis

The primary endpoint is defined as

- Change from baseline to Week 5 in the global score of the Wound-QoL questionnaire.

The primary endpoint will be analysed by the following primary analysis in the evaluable and completer populations.

Let μ be defined as expected value of change from baseline to Week 5 in the global score of the Wound-QoL questionnaire.

The null hypothesis to be tested is that μ is equal to 0, i.e., no score change from baseline. The alternative hypothesis is that μ is different from 0. i.e.:

$H_0: \mu = 0$ vs. $H_1: \mu \neq 0$.

The null hypotheses will be tested using a paired t-test statistic. The t-test is conducted using Proc MEANS procedure in SAS version 9.4. The null hypothesis will be rejected at a two-tailed significance level of 0.05.

In addition, descriptive statistics (n, mean, SD, median, min, max) will be provided in the evaluable population for the primary endpoint. Associated the 95% CI and p-value will be presented for the change from baseline to Week 5 in the global score of the Wound-QoL questionnaire.

The primary endpoint analysis will also be repeated using the safety and completer populations.

5.2.2 Secondary Variable(s)

The secondary endpoints are:

- Change from baseline to Week 5 in the Body subscore of the Wound-QoL questionnaire
- Change from baseline to Week 5 in the Psyche subscore of the Wound-QoL questionnaire
- Change from baseline to Week 5 in the Everyday Life subscore of the Wound-QoL questionnaire

All secondary endpoints will be analysed using the summary statistics primarily in the evaluable population. This analyses will be repeated using the safety and completer populations. For continuous variables, data will be summarized with the number of patients (n), mean, SD, median, minimum, and maximum. Wound-QoL questionnaire subscores are defined in the Appendix 1.

5.2.3 Exploratory Variable

The exploratory endpoint is:

- Change from baseline to Week 5 in the appearance and size of the target wound(s)

As each subject may have 2 chronic wounds, which will be treated and assessed, we will need to distinguish between the 2 wounds for the purpose of descriptive analysis (i.e. wound #1 and wound #2). The appearance of wound(s) includes categorical variables: surrounding erythema (yes, no), swelling categories, odor categories, and colour categories. The size of wound(s) is continuous variable measured in cm².

The continuous exploratory endpoint variable will be analysed by the summary statistics for each of the two wounds. Data will be summarized with the number of patients (n), mean, SD, median, minimum, and maximum. For categorical variables, frequency counts and percentages will be used to summarize the results. The number of non-missing values will be used as denominator in percentage calculations. To analyse change from the baseline for categorical

variables, the shift table from baseline to week 5 will be displayed for surrounding erythema and swelling for each of the two wounds.

This analysis will be conducted in the evaluable population and repeated using the completer population.

5.2.4 Subgroup Analysis

To analyse change from baseline for categorical variables, the shift table from baseline to Week 5 will be displayed for each of the 2 wounds and any additional subgroup analyses will be specified depending on the data observed. The global score and change from baseline in Wound-QoL questionnaire will be summarized by subgroup category and week in the evaluable population.

5.2.5 Other Variables

There will be no hypothesis test for other variables, thus all of them will be conducted based on descriptive statistics. The other variables to be analysed are:

- Weekly global score and its change from baseline in Wound-QoL questionnaire
- Weekly Body subscore, Psyche subscore, and Everyday Life subscore and their change from baseline in Wound-QoL questionnaire
- Weekly appearance and size of wound(s)
- Weekly proportion of patients with no score of 3 or 4 given in each individual item in Wound-QoL questionnaire

The continuous variables global scores and size of wound(s) will be analysed by the summary statistics by week (weeks 1, 2, 3, 4, 5) with the number of patients (n), mean, SD, median, minimum, and maximum.

For categorical variable appearance of wound(s), frequency counts and percentages will be used to summarize the results by week. The number of non-missing values will be used as denominator in percentage calculations.

The first two analyses above will be conducted in the evaluable, safety and completer populations whereas the last two analyses will be conducted in the evaluable and completer populations.

5.2.6 Adverse Events

Any adverse event that occurs at or after first study treatment administration and up to the end of the study treatment is considered as treatment emergent adverse event (TEAE).

An adverse event starting before the first study treatment and worsened in intensity between the first administration of study treatment and the end of the study treatment will also qualify as a treatment emergent adverse event (TEAE).

Pre-existing diseases or conditions occurring before screening visit are considered to be medical history and should be recorded as TEAEs only if they worsen (untoward change in intensity, frequency, or quality) after the first study treatment.

For adverse events where the intensity changes over time, the maximum intensity observed during the whole duration of the adverse event will be documented and captured in the database. If the adverse event stopped and reoccurred with a different or the same intensity, it will be entered as new adverse event in the eCRF.

All AEs with start date after screening visit but before first study treatment administration and that do not worsen after the first study treatment administration, and all AEs with start date after the date of end study treatment will be regarded as non-TEAE. This study will not display non-TEAEs in the tables or listings.

In case of incomplete start/stop date, an AE will be considered as non-TEAE if this can be concluded without any doubt. All other cases will be considered TEAE occurred during the 4-week treatment period. The non-TEAEs will not be included in the AE analysis.

Related TEAEs are entered “yes” as documented in the eCRF.

The following overview table will be generated.

Summary of the number of patients with

- At least 1 TEAE
- At least 1 serious TEAE
- At least 1 related TEAE
- At least 1 TEAE leading to discontinuation from the treatment (i.e. TEAE with “Action take with Prontosan due to AE”: “stopped both”)
- A TEAE with a fatal outcome

Unless stated otherwise, the following TEAE summaries will be presented:

The number and percentage of patients with serious TEAEs will be summarized by System Organ Class (SOC) and PT (sorted alphabetically).

The percentage denominator will be the number of patients in the safety population.

Adverse Device Effects (ADEs) are considered as AEs that are related to the study device. The possible anticipated ADEs with Prontosan solution or Prontosan gel include AEs: burning sensation, itching, and rash. The suspected unexpected serious adverse reactions (SUSARs) are

serious ADEs that have not previously been documented in the protocol or other safety information.

The number and percentage of patients with ADEs will be summarized by SOC and PT (sorted alphabetically) for each

- ADE
- Serious ADE

Only serious AEs and ADEs will be coded according to MedDRA, version 20.0 or higher. All AEs will be listed. All AE analysis will be conducted in the safety population.

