9.2.5 Week 5 (Final Visit: End of Treatment or Early Discontinuation)

At the Week 5 visit (final visit: end of treatment or early discontinuation), the following assessments will be performed by the Investigator or designee:

- Ask the patient to complete the Wound-QoL questionnaire before any other visit assessment.

- Review the diary and examine used bottles and any unused bottles of study treatment.
- Record concomitant medications.
- Measure vital signs (blood pressure, pulse, temperature).
- Collect blood for measuring HbA1c and for standard hematology and serum chemistry parameters.
- Perform a brief physical examination.
- Assess the wound(s) appearance, granulation tissue, exudate, drainage, surrounding erythema and/or swelling, and any signs of infection.
- Measure the wound(s) size pre-treatment (pre-debridement) with a standard, single-use, disposable ruler using the clock method (see Section 10.3 and Section 15, Appendix 2).
- Photograph the wound(s) pre-treatment (pre-debridement) using the study camera and a standard, single-use, disposable ruler to indicate relative size.
- Clean the wound(s) and wound area(s) with Prontosan solution per the institutional guidelines and Prontosan IFU for the individual patient wound(s).
- Assess the patient for any AEs.
- Measure the wound(s) size post-cleaning (post-debridement) with a standard, single-use, disposable ruler using the clock method.
- Photograph the wound(s) post-cleaning (post-debridement) using the study camera and a standard, single-use, disposable ruler to indicate relative size.
- Apply Prontosan gel to the wound(s) and apply the bandage/dressing per the institutional guidelines and the Prontosan IFU for the individual patient wound(s).

Patients who prematurely withdraw from the study for any reason should complete these early discontinuation visit requirements. If the early discontinuation visit is not done, the reason(s) will be recorded in the eCRF. Patients who withdraw or are withdrawn before completion of the Week 2 assessments and the Week 3 Wound-QoL questionnaire will be replaced to ensure that at least 52 patients will complete the study.

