12.6 Safety Analysis

All reported AEs will be coded using the Medical Dictionary for Regulatory Activities. The incidence of TEAEs (events with onset dates on or after the start of the study treatment) will be included in incidence tables. Events with missing onset dates will be included as treatment-emergent. If a patient experiences more than 1 occurrence of the same AE, the occurrence with the greatest severity and the closest association with the study device will be used in the summary tables. SAEs, AEs causing discontinuation, and ADEs will be tabulated. All AEs will be listed by patient, along with information regarding onset,

duration, severity, relationship to study device, action taken with study device, treatment of event, and outcome.

Clinical laboratory data, vital signs, physical examination results, wound history, and medical history will be listed by patient.

Listings and summary tables will be provided for prior medications and for concomitant medications initiated or continued during the study period. Study treatment exposure will be listed by patient and summarized descriptively.

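### The SAP closes the treatment-emergent window at an undefined end of study treatment, conflicting with the protocol's definition and with the SAP's own rules on listing events and on device effects

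*SAP*

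**What the plan says.** **Protocol.** Section 12.6 sets a start for treatment emergence but no end: "The incidence of TEAEs (events with onset dates on or after the start of the study treatment) will be included in incidence tables". It also requires every AE to be listed by patient. Section 11.4.1 sets the AE collection period from informed consent to the final visit. Section 12 gives the SAP precedence wherever the two documents differ.

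**SAP 5.2.6, exclusion rules.** The section opens with a closed window for TEAEs: "Any adverse event that occurs at or after first study treatment administration and up to the end of the study treatment is considered as treatment" (the sentence goes on to name the TEAE category). It then states the consequence for later onsets: "all AEs with start date after the date of end study treatment will be regarded as non-TEAE". Two further sentences say what happens to those events: "This study will not display non-TEAEs in the tables or listings" and "The non-TEAEs will not be included in the AE analysis".

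**SAP 5.2.6, later paragraphs.** The same section defines device effects by relatedness only: "Adverse Device Effects (ADEs) are considered as AEs that are related to the study device". It closes with an unqualified listing rule: "All AEs will be listed".

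**SAP section 6.** Table 11.1 is the TEAE overview and Table 12.2 the serious TEAEs. Tables 11.2, 12.1 and 12.3 cover ADEs. Listings 10.1 and 10.2 cover AEs and ADEs.

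**The concern.** The SAP narrows the protocol's TEAE definition without giving a reason, and the narrower rule governs. Its cut-off depends on a term that the SAP leaves undefined. If *end of study treatment* means the last application, a patient who stops product and is seen some days later has an interval in which AEs are collected but cannot count as treatment-emergent. A serious event in that interval would still go to the sponsor within 24 hours under protocol 11.4.3, yet it would be absent from the serious TEAE table.

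The SAP also gives a programmer two incompatible instructions. A related rash with onset in that interval is barred from all tables and listings by one paragraph. Under another it is an ADE, to be tabulated and listed. It could appear in Table 11.2 while missing from the related-TEAE row of Table 11.1.

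**Working it through.** The plan gives no figure for this point, so the check is mainly a comparison of dates and rules.

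**1. Three dates decide whether an event is lost.**

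- L: date of last application.
- V: date of the final or early discontinuation visit, when AE collection ends (protocol 11.4.1).
- E: the SAP's date of end of study treatment, which could be L or V.

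An event with start date S is collected if it starts by V. The SAP rule removes it if S is later than E. The interval of collected but excluded onsets is therefore V − E.

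**2. Patients who complete Week 5.** Protocol 6.1 and 9.2.5 place the last treatment at the Week 5 visit, so L = V and V − E = 0 days under either reading. The cut-off is by calendar date, so a reaction later on the day of the last application is still a TEAE. Restoring the protocol definition adds no collected event here.

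**3. Patients whose last application precedes their final visit.** Hypothetical case: product stopped on day 10, AE onset on day 11, early discontinuation visit on day 14.

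| Meaning of end of study treatment | E | Excluded interval | AE on day 11 |
|---|---|---|---|
| Last application, none given at the visit | day 10 | 14 − 10 = 4 days | non-TEAE |
| Final or early discontinuation visit | day 14 | 0 days | TEAE |
| Last application, given at the visit | day 14 | 0 days | TEAE |

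The event is collected in all three rows. Only the first loses it.

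**4. Where a lost event would be missing.**

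| Output | Exclusion paragraphs of SAP 5.2.6 | Later paragraphs of SAP 5.2.6 | Protocol 12.6 |
|---|---|---|---|
| TEAE overview (11.1), serious TEAEs (12.2) | out | silent | in |
| ADE tables (11.2, 12.1, 12.3), if related | out | in | in |
| AE listing (10.1) | out | in | in |

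The first row is a clear exclusion. The other two are contradictions within the SAP. The listing conflict also covers AEs that start between consent and first treatment, which the exclusion paragraphs bar as non-TEAEs too.

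**5. Size.** The documents give neither a rate of early stopping nor the length of the interval. As an assumption only, if 0%, 5%, 10% or 20% of 52 treated patients stopped product before their final visit, then 52 × 0 = 0, 52 × 0.05 = 2.6, 52 × 0.10 = 5.2 or 52 × 0.20 = 10.4 patients would be exposed to the rule. These are patients who could lose an event, not events lost.

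Per patient-level event lost, the incidence falls by 1/52 = 1.9 percentage points. The 52 is the number meant to complete the study. The safety population is everyone treated, and early withdrawals are replaced, so the denominator may be larger. With 10 further treated patients, for example, the figure is 1/62 = 1.6 points.

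**The case against.** The strongest defence is that there may be no gap. The protocol labels the final visit as end of treatment, and Table 1 extends that label to the early discontinuation visit. If the SAP means the same, its window closes when AE collection closes. The early discontinuation visit also carries the Week 5 procedures, including cleaning with the solution and applying the gel. Followed literally, that makes the last application coincide with the visit. Both readings are possible. Neither is stated in the SAP, and the documents do not say whether someone who stopped product because of an AE is treated again at that visit. The defence shows that the term is undefined; it does not show that the rule is harmless.

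The SAP's precedence over the protocol is also a fair point, but it makes the narrower rule binding and cannot resolve a conflict inside the SAP.

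Three stronger readings are tempting, and the documents do not support them:

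- *Late reactions disappear from every AE analysis.* For the ADE tables and the AE listings, the SAP contradicts itself rather than clearly excluding them.
- *Reported rates are biased low because early stoppers are the patients most likely to react.* Nothing in the documents says so. A reaction that causes stopping normally starts before the stop, and so is already a TEAE.
- *The final gel application goes unassessed in all patients.* Protocol 9.2.5 lists the AE check before the gel step, but it fixes order expressly only for the questionnaire. List order alone does not establish that the application is unassessed.

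**Conclusion.** The point holds in a limited form. SAP 5.2.6 conflicts with protocol 12.6 over the end of the TEAE window and over listing, and it conflicts with itself over listing and ADEs. The conflicts are on the page and need no assumption.

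The loss of events is conditional. It requires that end of study treatment means the last application, and that some patients have their last application before their final or early discontinuation visit. For those patients, collected events with a start date after the last application would be missing from Tables 11.1 and 12.2. Completers treated at Week 5 are unaffected. The total effect cannot be computed from the documents; the effect per lost patient-level event is about 1.9 percentage points if about 52 patients are treated, and less if more are. This is a safety-reporting defect that should be corrected. It has no bearing on the primary endpoint or on the collection and expedited reporting of serious events.

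**What to change.** In SAP 5.2.6:

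1. Define a TEAE as any AE with onset or worsening on or after first study treatment, through the final or early discontinuation visit. This matches the end of AE collection in protocol 11.4.1. Apply the same end to worsening of earlier events and pre-existing conditions, which the section now treats in two different ways.
2. Delete the rule that makes AEs after the end of study treatment non-TEAEs.
3. Reconcile the exclusion paragraphs with the later paragraphs and with protocol 12.6, so that all collected AEs are listed and every AE marked related is tabulated as an ADE, whatever its onset relative to the last application.

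The cost is SAP wording and the matching table programming, with no added visit or procedure. The reported TEAE incidence may be slightly higher. Capturing onsets after the final visit would be a different change, because it would need a longer AE collection period in the protocol, and it is not proposed here.

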	8. Efficacy - Wound measurement
Table 8.1	Wound measurement – descriptive statistics – Evaluable Population
Table 8.2	Wound measurement – descriptive statistics – Completer Population
	9. Efficacy –Exploratory
Table 9.1	Surrounding erythrema – change from baseline to week 5 - Evaluable Population
Table 9.2	Swelling – change from baseline to week 5 - Evaluable Population
	10. Efficacy –Other exploratory
Table 10.1	Proportion of patients with no score of 3 or 4 given in any individual item of the Wound-QoL questionnaire – Evaluable Population
Table 10.2	Proportion of patients with no score of 3 or 4 given in any individual item of the Wound-QoL questionnaire – Completer Population
	11. Display of adverse events
Table 11.1	Overview of the number of subjects with TEAEs – Safety Population
Table 11.2	Overview of the number of subjects with ADEs – Safety Population
	12. AEs by SOC and PT
Table 12.1	ADEs by primary SOC and PT – Safety Population
Table 12.2	Serious TEAEs by primary SOC and PT – Safety Population
Table 12.3	Serious ADEs by primary SOC and PT – Safety Population
	13. Laboratory value
Table 13	Laboratory samples – descriptive statistics – Safety Population

Listings

	1. Subject disposition
Listing 1.1	Subject completion/discontinuation – Enrolled Population
Listing 1.2	Subject allocation to study population – Enrolled Population
	2. Protocol deviations
Listing 2	Protocol deviations – Enrolled Population
	3. Subjects excluded from analysis
Listing 3	Violation of in-/exclusion criteria – Enrolled Population
	4. Demographic data and baseline background characteristics
Listing 4	Demographic and baseline background data – Enrolled Population
	5. Medical history
Listing 5	Prior and concomitant illnesses – Safety Population
	6. Wound history
Listing 6	Wound history - Safety Population
	7. Prior and concomitant medications
Listing 7	Prior and concomitant medications – Safety Population
	8. Study medication exposure
Listing 8	Exposure – Safety Population
	9. Wound assessment
Listing 9.1	Wound assessment - Safety Population
Listing 9.2	Wound measurement - Safety Population
	10. Adverse event
Listing 10.1	Adverse events – Safety Population
Listing 10.2	Adverse device effects – Safety Population
	11. Laboratory data
Listing11	Laboratory values – Safety Population
	12. Vital signs
Listing 12	Vital signs values – Safety Population
	13. Physical examination
Listing 13	Physical examination – Safety Population

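### SAP 5.2.6 gives two incompatible rules on listing AEs outside the treatment-emergent window, and it narrows protocol 12.6's AE coding and SAE tabulation without marking the change

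*SAP*

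**What the plan says.** SAP 5.2.6 defines non-TEAEs as events that start after screening but before first treatment and do not worsen afterwards, together with events that start after the end of treatment. It says of them that "This study will not display non-TEAEs in the tables or listings" and that "The non-TEAEs will not be included in the AE analysis". Towards the end of the same section it says "All AEs will be listed". In SAP section 6, Listing 10.1 is titled "Adverse events – Safety Population", with no treatment-emergent limit.

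On coding, the SAP says "Only serious AEs and ADEs will be coded according to MedDRA, version 20.0 or higher". Its SOC/PT tables are 12.1 (ADEs), 12.2 ("Serious TEAEs by primary SOC and PT") and 12.3 (serious ADEs). The only display of TEAEs as a whole is Table 11.1, "Overview of the number of subjects with TEAEs".

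Protocol 12.6 is wider. It codes every reported AE in MedDRA, puts TEAE incidence into incidence tables, and fixes which occurrence counts when a patient has the same AE more than once. It tabulates SAEs, AEs causing discontinuation and ADEs, and lists every AE by patient. Protocol 11.4.1 collects AEs from consent to the final visit. Protocol 11.4.3 requires every SAE during the study to be entered on the AE eCRF. Protocol section 12 lets the SAP prevail where the two documents differ.

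**The concern.** A programmer building Listing 10.1 has two instructions from one section of the SAP and no basis in the SAP for choosing. One choice leaves collected safety events, possibly serious ones, out of every AE output.

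The coding change has a different effect. Whether a non-serious event is coded and counted by term depends on a single yes/no relatedness judgement by the investigator. In an open-label study with one arm there is no comparator against which to check that judgement. Because the SAP prevails over the protocol, its narrower rules would govern the report, and a reader of the protocol would not know that they had changed.

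**Working it through.** No design figure bears on this point. The check sets the texts side by side and counts outputs.

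**Step 1. Rules compared**

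| Item | Protocol | SAP 5.2.6 and section 6 |
|---|---|---|
| Collection | From consent (11.4.1) | Recognises AEs that start before first treatment |
| Listing | All AEs by patient (12.6) | Non-TEAEs in no listing; also, all AEs listed; Listing 10.1 not limited to TEAEs |
| Coding | All reported AEs (12.6) | Serious AEs and ADEs only |
| TEAE incidence | Incidence tables with a counting rule for repeats of one AE (12.6) | Overview counts for all TEAEs; SOC/PT only for ADEs, serious TEAEs and serious ADEs |
| SAEs | Tabulated, no treatment-emergent limit stated (12.6) | Serious TEAEs only (Table 12.2) |

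**Step 2. Treated patient with an SAE before first treatment that does not worsen**

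- AE tables: 11.1, 11.2, 12.1, 12.2, 12.3 = 5. The event is not a TEAE, is not a device effect, and is excluded from the AE analysis: 0 of 5.
- AE listings: 10.1 and 10.2 = 2. If the non-display rule prevails: 0 of 2. If the all-AEs rule prevails: 1 of 2 (Listing 10.1).

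The same count applies to a non-serious AE in that interval.

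**Step 3. TEAEs by seriousness and relatedness**

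| TEAE | SOC/PT tables | MedDRA coded |
|---|---|---|
| Serious, related | 12.1, 12.2, 12.3 | Yes |
| Serious, unrelated | 12.2 | Yes |
| Non-serious, related | 12.1 | Yes |
| Non-serious, unrelated | None | No |

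The 3 SOC/PT tables cover 3 of the 4 cells, and 0 of the 5 AE tables show all TEAEs by term. Events in the fourth cell reach the AE outputs only through the Table 11.1 counts and, uncoded, Listing 10.1.

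**Step 4. Length of the interval**

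Protocol 9.2.1 puts baseline 1 week ± 1 day after screening, so 6 to 8 days. With Week 5 nominally 28 days ± 1 day after baseline, the pre-treatment share of the collection period is 7/(7 + 28) = 20%, with a range from 6/(6 + 29) = 17% to 8/(8 + 27) = 23%. SAP 5.1.4 words the interval as at most one week, which would allow a smaller share. This is a share of observation time, not a forecast of events.

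**The case against.** The best defence of the listing rule is that a specific rule governs a general one. The sentence that all AEs will be listed follows directly after the coding sentence, so it may mean all analysed AEs, coded or not. That reading is possible. It is also true that every TEAE is in Listing 10.1 either way, so only non-TEAEs are affected. But the SAP writes TEAE in the titles of Tables 11.1 and 12.2 where it means that limit and does not write it in Listing 10.1, and the protocol lists every AE.

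The SAP is entitled to supersede the protocol, so narrower coding and tables are not forbidden. This stands. It does not resolve a conflict between two SAP sentences, and it makes an unmarked change matter more. Front matter of the SAP was not available, so the absence of a flag is judged on the text supplied.

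Protocol 12.6 does not use the words by term, and its SAE sentence could be read as confined to TEAEs because it follows the TEAE sentences. Both points stand. Tables by term are implied by coding all AEs and by the rule for repeats of the same AE, but they are not stated. With about 52 patients, a reader can also inspect the whole listing, though uncoded terms cannot be grouped without later coding.

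Three stronger readings are tempting, and the documents do not support them.

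- A reader might infer that a pre-treatment SAE would surface only in Listing 5, "Prior and concomitant illnesses – Safety Population", uncoded and not marked as serious. Protocol 11.4.3 puts every SAE on the AE eCRF, and the SAP codes serious AEs without limiting this to TEAEs.
- A reader might infer that protocol Table 1, which first assesses AEs at baseline, contradicts collection from consent. A baseline review can capture events since consent.
- A reader might use the wound-infection figure in protocol 4.3 (29/953, 3%) to size the gap. It comes from a retrospective review with follow-up per patient not stated, whereas this trial excludes infected wounds at entry. It would give the frequency of any infection, not of one rated both non-serious and unrelated. An infection that ended participation would also be in Listing 1.1.

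**Conclusion.** The point holds. SAP 5.2.6 contradicts itself on listing non-TEAEs. For a treated patient whose AE or SAE starts between consent and first treatment and does not worsen, the outcome is 0 of 5 AE tables under either rule, and 0 or 1 of 2 AE listings depending on which rule is followed. Separately, the SAP replaces coding of all AEs with coding of serious AEs and ADEs, so one of the four seriousness-by-relatedness cells has no SOC/PT display, and it limits the SAE table to serious TEAEs. None of this is marked as a change in the SAP text supplied.

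The conclusion on tables by term rests on an inference from protocol 12.6, and the conclusion on SAEs rests on the absence of a stated limit there. The number of events affected cannot be estimated from the documents. The primary endpoint is untouched. This is a correction to safety reporting that should be made before the outputs are programmed.

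**What to change.** - Delete the non-display sentence from SAP 5.2.6 and list all AEs in Listing 10.1 with a flag for pre-treatment, treatment-emergent or post-treatment.
- Code all AEs as protocol 12.6 states, and add one table of all TEAEs by SOC and PT in the Safety Population.
- List or tabulate SAEs outside the treatment-emergent window.
- Reconcile protocol 8.4.1, which treats new illnesses between consent and first treatment as concomitant illnesses, with protocol 11.4.1, which collects AEs from consent, so that sites record such events in one way.
- If the sponsor keeps the narrower coding and tables, state this in the SAP as a change from protocol 12.6 and give the reason. The listing conflict still has to be resolved.

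The cost is MedDRA coding of the remaining AEs in about 52 patients plus replacements, one or two extra outputs, and revised wording.
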